5.0 STATISTICAL PLAN

5.1 Sample Size Determination

The overall objective of the trial is to determine the most effective alcohol-based pre-operative antiseptic skin solution for use during extremity fracture management. This objective is being performed independently in the open and closed fracture populations. In both fracture populations, the analyses will compare the effectiveness of iodine povacrylex (0.7% free iodine) in 74%

isopropyl alcohol versus 2% CHG in 70% isopropyl alcohol surgical skin preparations. The primary outcome is the occurrence of SSI, as per the adapted CDC criteria (**Table 3**).²⁵ The secondary outcome is the occurrence of unplanned fracture-related reoperations within 12 months of injury. Separate sample size estimates for the open and closed fracture populations were calculated to facilitate the primary comparison between proportions of patients with SSI in each treatment group. It is expected that this estimate will also provide adequate power for the secondary outcome (unplanned fracture-related reoperation) because a meaningful effect size for the reoperation outcome is expected to be similar to the SSI estimates. Additionally, the baseline risk of unplanned reoperations in both fracture populations is expected to be greater than the risk of SSI.⁴

Assuming an ITT principle for the analysis, the sample size was calculated based on a cluster crossover design with the cluster as the unit of randomization and the patient as the unit of analysis. For complex study designs, such as a cluster-randomized crossover trial, simple formulas to calculate sample size or power may not capture the expected variability from the observed data.⁴⁵ Simulation methods were used to obtain empirical power calculations based on a feasible number of recruiting clusters and the expected number of participants within the open and closed fracture populations.⁴⁵ The simulation estimates are designed to detect a difference between the treatment groups, accounting for between hospital variability inherent to a cluster-crossover trial design.

We have estimated the CHG group will experience a SSI incidence of 12.5% in the open fracture population and a 3.5% incidence within the closed fracture population.^{3,4} Compared to CHG, we have assumed the iodine povacrylex solution will achieve a 0.65 risk reduction for SSI and unplanned fracture-related reoperation in each fracture population.²² This effect was selected as the smallest difference that would be important to detect, in the sense that any smaller effect would not be of clinical or substantive importance. Additionally, this effect was deemed more conservative than data reported by Swenson et al. and was consistent with feasible recruitment goals.²¹

We have based our sample size assumptions using a single crossover, 2-period design to ensure the most conservative sample size estimate. Recent simulation data suggest that increasing the number of period crossovers can increase the statistical power of a given sample size.⁴⁶ The initial power estimate assumed 10 recruiting clusters, a 10% loss to follow-up rate,⁴ and applying the between-cluster variance of 0.095 observed in the FLOW trial. Based on enrollment of a minimum of 1,540 open fracture patients and 6,280 closed lower extremity and pelvic fractures, greater than 80% power would be achieved for each fracture population. Subsequent to the initial power calculations, the early trial experience demonstrated a need to increase the number of clusters to obtain a feasible recruitment pace. As a result, a minimum 18 clusters will enroll participants into PREPARE. The increase in clusters results in a marginal increase in power (~2%).

Table 5 and **Table 6** below outlines the summary of the initial sample size assumptions. These sample size estimates are rounded up to the nearest multiple of 20 to ensure balance among 10 clinical sites and two interventions.

Table 5: Sample Size Assumptions for Open Fractures

Baseline SSI Risk	Iodine Risk Ratio	Iodine Odds Ratio	Sample Size	Sample Size Increased by 10%
-------------------	-------------------	-------------------	-------------	------------------------------

10.0%	0.62	0.59	1,600	1,760
10.0%	0.65	0.63	1,960	2,100
10.0%	0.67	0.65	2,200	2,420
10.0%	0.70	0.68	2,600	2,860
12.5%	0.62	0.59	1,300	1,440
12.5%	0.65	0.62	1,400	1,540
12.5%	0.67	0.64	1,600	1,760
12.5%	0.70	0.67	1,800	1,980
14.0%	0.62	0.58	1,200	1,320
14.0%	0.65	0.61	1,300	1,440
14.0%	0.67	0.64	1,500	1,660
14.0%	0.70	0.67	1,800	1,980

Note: Between cluster ICC = 0.028; Between cluster variance = 0.095; Between period variance = 0; Number of clusters = 10; Number of periods = 2; Alpha = 0.05

Table 6: Sample Size Assumptions for Closed Fractures of the Lower Extremity

Baseline SSI Risk	Iodine Relative Risk	Iodine Odds Ratio	Sample size	Sample Size increased by 10%
2%	0.62	0.62	8,200	9,020
2%	0.65	0.65	10,000	11,000
2%	0.67	0.67	11,400	12,540
3.5%	0.62	0.61	4,700	5,170
3.5%	0.65	0.64	5,700	6,280
3.5%	0.67	0.66	6,600	7,260
5%	0.62	0.61	3,300	3,640
5%	0.65	0.64	4,100	4,520
5%	0.67	0.67	4,300	4,740

Note: Between cluster ICC = 0.028; Between cluster variance* = 0.095; Between period variance = 0; Number of clusters = 10; Number of periods = 2; Alpha = 0.05

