Several strategies may be used to maximize follow-up including: 1) at the time of enrollment, each participant will provide their own telephone number, as well as the name and address of a primary care physician, and the names and phone numbers of three people at different addresses with whom the participant does not live with and who are likely to be aware of the participant's whereabouts; 2) participants will receive a reminder card upon discharge for their next follow up visit by the clinical site study personnel; 3) participants will receive text message reminders; 4) follow-up will coincide with normal surgical fracture clinic visits; and 5) if a participant refuses or is unable to return for the follow-up assessment, study personnel will determine his/her status with regard to major study outcomes by telephone, text, mail, or email contact with the participant or the provided alternate contacts. Given these are standard of care visits and the participants will be receiving ongoing orthopaedic care for their acute fractures, minimal loss to follow-up is expected. Using these techniques, we expect greater than 95% follow-up at 3 months and 90% follow-up at 12 months post-fracture.

Participants will not be deemed lost to follow-up until the 12-month visit is overdue and all attempts to contact the participant have been exhausted. Participants will not be withdrawn from the study if the study protocol was not adhered to (e.g., allocated treatment not received, missed follow-up visits, etc.). The reasons for participants being withdrawn from the study will be documented (e.g., withdrawal of consent or lost to follow up).

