5.2.2 Analysis of the Study Outcomes

Adopting an ITT principle, multilevel regression models will be used. Correlation structures will be fit based on the observed between cluster and between period effects. A robust sandwich estimator will be used to analyze the primary and secondary outcomes.

For the primary outcome, SSI will be the dependent variable and the antiseptic solution (treatment group) will be the independent variable. For the secondary outcome, unplanned fracture-related reoperation will be the dependent variable and the antiseptic solution (treatment group) will be the independent variable. For both analyses, multiple imputation will be used to handle missing data.⁵¹

As the optimal methods for analyzing cluster crossover trials continue to evolve, the final statistical modeling technique to be used will be determined in accordance with contemporary best practices prior to the completion of participant follow-up. A separate Statistical Analysis Plan will be developed prior to study closeout. **Table 7** below shows a summary of the study outcomes, corresponding hypotheses, and currently proposed methods of analysis.

Table 7: Summary of Outcome Analysis Plan

Objective	Outcome		Hypothesis	Method of Analysis
	Name	Type		
To determine the effect of iodine-based versus CHG-based pre-operative antiseptic skin solutions on the incidence of SSI and unplanned fracture-related reoperation.	SSI	Binary	Iodine solution will be more effective than CHG solution	Multi-level regression model
	Unplanned Fracture-Related Reoperation	Binary	Iodine solution will be more effective than CHG solution	Multi-level regression model

Note: CHG = chlorhexidine gluconate; SSI = Surgical Site Infection

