### **1.3 Reporting**

The structure of this statistical analysis plan follows the Guidelines for the Content of Statistical Analysis Plans in Clinical Trials. The reporting of the trial results will follow the 2010 CONSORT statement and the extension statements for Cluster Trials and Randomized Crossover Trials, as applicable. Additional statistical analyses plans will be developed for secondary analyses of the trial data.

1    **2.0 STUDY METHODS**

2    **2.1 Trial Design**

3    The study is a pragmatic, multicentre, open-label, randomized multiple period cluster crossover  
4    trial. We defined clusters as orthopaedic practices within participating hospitals, with each  
5    participating hospital having only one participating orthopaedic practice. The intervention  
6    periods are approximately 2 months in length. After completing a 2-month period, the participating  
7    cluster crosses over to the alternative intervention where they use the other study solution for the  
8    next 2-month period. There are no washout periods between treatment periods.

9

10    **2.2 Randomization**

11    The order of treatment allocation for each orthopaedic practice (cluster) will be randomly assigned  
12    using a computer-generated randomization table. Each cluster will start with the initially allocated  
13    study solution and crossover to the other solution for their second recruitment period. This process  
14    of alternating treatments will repeat approximately every 2 months as dictated by the initial  
15    randomization until enrollment targets are met. The randomization will be in a 1:1 ratio,  
16    unrestricted, and executed only prior to the first sequence.

17

18    **2.3 Sample Size**

19    A sample size of 1540 patients will have 80% power to detect a 38% reduction in the odds of  
20    infection with a two-sided alpha of 0.05. This estimate allows for a 10% loss to follow-up and  
21    assumes a baseline infection risk of 12.5%, 10 recruiting clusters, no between-period variance, and  
22    a 0.095 between-cluster variance. After the initial power calculations, we determined that  
23    additional clusters were required to meet the study timelines. As such, we increased the number of

24 clusters from 10 to a minimum of 22. The increase in clusters results in a marginal increase in  
25 statistical power (approximately 2%).

26

27 **2.4 Framework**

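### Open-fracture power is overstated: 1,540 enrolled with the stated 10% loss gives about 76–77% power for an odds ratio of 0.62, not 80% or more

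*Protocol*

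**What the plan says.** Protocol 5.1 bases the open-fracture minimum on a chlorhexidine infection risk of 12.5%. It calls the assumed effect the smallest difference important to detect. The design inputs are given as "The initial power estimate assumed 10 recruiting clusters, a 10% loss to follow-up rate" with a between-cluster variance of 0.095, and the note to Table 5 adds "Between period variance = 0; Number of clusters = 10; Number of periods = 2; Alpha = 0.05". The relevant Table 5 row (12.5%, risk ratio 0.65, odds ratio 0.62) lists 1,400 patients, raised by 10% to 1,540. From this the Protocol concludes that "greater than 80% power would be achieved for each fracture population".

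The PREPARE Open SAP, section 2.3, repeats the claim: "A sample size of 1540 patients will have 80% power to detect a 38% reduction in the odds of" infection, two-sided alpha 0.05, allowing for 10% loss and assuming 10 clusters. Both documents then credit extra clusters (at least 18 in the Protocol, at least 22 in the Open SAP) with about 2% more power.

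The Protocol says that power was simulated but does not name the test used. Its analysis section (5.2.2) states: "A robust sandwich estimator will be used to analyze the primary and secondary outcomes".

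**The concern.** With zero between-period variance, each cluster's effect cancels when its two periods are compared, so power should be close to that of an individually randomised comparison of two proportions. On that basis 1,400 evaluable patients look too few for 12.5% versus 8.125%. The loss allowance also does not return what it should: 90% of 1,540 is below 1,400.

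Because the assumed effect is described as the smallest that matters, the stated power tells readers how much weight a null open-fracture result can bear. An overstated figure makes such a result look more conclusive than it is.

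**Working it through.** **Inputs** (Protocol 5.1, Table 5 and its note; Open SAP 2.3): p1 = 0.125; risk ratio 0.65, so p2 = 0.08125 (odds ratio 0.619, listed as 0.62); two-sided alpha 0.05; 1:1 allocation; 10 clusters × 2 periods; between-cluster variance 0.095; between-period variance 0; loss 10%.

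**1. The plan's own sample size.** 1,400 × 1.10 = 1,540. Ten per cent loss leaves 1,540 × 0.90 = 1,386, which is 14 fewer than the 1,400 intended. Dividing instead gives 1,400 / 0.90 = 1,556.

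**2. Power by formula at 1,386 (693 per arm).** Power = Φ(|p1 − p2| / SE − 1.960).
- SE = √[(0.125 × 0.875 + 0.08125 × 0.91875) / 693] = √[(0.109375 + 0.074648) / 693] = 0.01630
- 0.04375 / 0.01630 = 2.685
- Power = Φ(2.685 − 1.960) = 76.6%

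The pooled-variance form gives 76.4% and the log odds ratio form 75.8%.

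**3. Other evaluable numbers.**

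| Evaluable | Meaning | Formula | Simulation |
|---|---|---|---|
| 1,386 | 10% loss | 75.8–76.6% | 76.1–77.0% |
| 1,400 | Table 5 entry | 76.2–77.0% | 76.8–77.4% |
| 1,463 | 5% loss | 78.0–78.8% | 78.1–79.4% |

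If all 1,540 were evaluable, power would be 80.0–81.2%. The stated 80% is recovered only there.

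The simulations used the stated design, 20,000 trials (Monte Carlo standard error 0.3 point) and a cluster-stratified test. At 1,386 the two ends are 77.0% when 12.5% is the average-cluster risk and 76.1% when it is the population-average risk. Null rejection was 5.1% and 4.9%. A separate simulation with a random-intercept logistic model gave 75.9–76.7% at 1,380 and 79.8–80.5% at 1,540.

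**4. Evaluable number needed for 80%.** N = 2 × (1.960 + 0.842)² × (0.109375 + 0.074648) / 0.04375² ≈ 1,509. The pooled form gives 1,516, and about 1,490 suffices if 12.5% is the average-cluster risk. Dividing 1,490–1,516 by 0.90 gives about 1,655–1,685 enrolled.

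**5. Comparison within Table 5.** Scaling the other risk ratio 0.65 rows to 12.5% by the ratio of required sizes:
- from the 10% row: 1,960 × (1,509 / 1,932) = 1,531. The inflated entry of 2,100 does not match 1,960 × 1.10 = 2,156; if 1,900 was meant, the result is 1,484.
- from the 14% row: 1,300 × (1,509 / 1,328) = 1,477.

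Both exceed 1,400. The other rows at 12.5%, by the unpooled formula:
- risk ratio 0.62: 1,300 listed, 81.3% power, adequate;
- risk ratio 0.67: 1,600 listed, 77.2% power, about 1,717 needed;
- risk ratio 0.70: 1,800 listed, 73.4% power, about 2,112 needed. The 14% baseline row also lists 1,800, although it needs only 1,858.

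**6. Relative size of the two causes.** The row itself (1,400 against roughly 1,500) costs about 3 points. The loss inflation (1,386 against 1,400) costs about 0.4 point.

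**The case against.** The strongest objection is that power was simulated and neither the test nor the code is given. If the test was the sandwich z-test suggested by Protocol 5.2.2, the table is nearly reproduced: taking 12.5% as the average-cluster risk, it gives 79.6% at 1,400, 79.1% at 1,386 and 81.0% at 1,463, and the risk ratio 0.67 row reaches 80.2%. That may well explain the entries. But with 10 clusters this test rejects a true null about 9.7–9.8% of the time, so the figure is bought by breaking the stated alpha of 0.05. Referred instead to a t distribution on 9 degrees of freedom, it holds 5% but gives only 65.8–66.8%. Even the z version stays below 80% at 1,386, and it leaves the risk ratio 0.70 row at 76.9%.

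Other points carry some weight:
- *Follow-up.* For the infection window the Protocol says "we expect greater than 95% follow-up at 3 months and 90% follow-up at 12 months post-fracture". At 5% loss, power with a test that holds alpha is about 79%, so the expected shortfall is nearer one point. Both power claims nevertheless rest on 10%.
- *More clusters.* Granting the full 2 points still leaves about 79%. The gain depends on the test: from 10 to 22 clusters, the stratified test moves from 77.0% to 77.6% or from 76.1% to 75.7%, and the sandwich t-test from 66.8% to 73.1%.
- *1,540 is a minimum.* True, and over-enrolment would restore 80%, but both statements are about that minimum.
- *Covariate adjustment in the SAP model.* It may add some power, but it is not part of the stated calculation.
- *Internal scaling of Table 5.* The entries are coarse and the scaling uses the two-proportion formula, so this is supporting evidence rather than independent proof.

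**Conclusion.** The concern holds. On the documents' own inputs, the open-fracture minimum gives about 76–77% power after 10% loss, 3–4 points below the 80% in the Open SAP and further from the Protocol's claim of more than 80%. The chance of missing the target effect is about 23–24%, rather than 20% or less.

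This assumes a two-sided test that actually holds 5%, 1:1 allocation, and the stated variance components. The sponsor's simulation test is unknown, but no standard two-sided test holding 5% that was tried reached 80% at 1,386. The shortfall is modest and changes no design or analysis choice; the published figure is wrong as written. The finding is confined to the open-fracture population.

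**What to change.** No extra enrolment is requested.

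1. In Protocol 5.1 and Open SAP 2.3, state for the open population: *With the minimum 1,540 enrolled and 10% loss (1,386 evaluable), power is about 77% for an odds ratio of 0.62 at 12.5% chlorhexidine risk, and about 79% at 5% loss; 80% power is available for a risk ratio of about 0.636 (odds ratio about 0.605).*
2. Correct the Table 5 rows at 12.5% baseline for risk ratios 0.65, 0.67 and 0.70, and inflate for loss by dividing by 0.90.
3. Name the test behind the simulated power and report its null rejection rate. Re-derive the 2% gain for the actual cluster counts (18 in the Protocol, 22 in the Open SAP), or drop it.
4. In Protocol 5.1, describe the effect as a risk ratio of 0.65. The text calls it a risk reduction of 0.65, whereas Table 5 uses 0.65 as the ratio, a 35% reduction.

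The cost is text and table edits, with a stated open-fracture power 3–4 points less favourable.

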5.2 Statistical Methods

5.2.1 Analysis Plan Overview

A detailed statistical analysis plan will be published prior to the completion of the trial. The following analysis plan will be conducted independently for the open and closed fracture populations. For each population, the analyses and reporting of the results will follow the CONSORT guidelines for reporting of both pragmatic trials⁴⁷ and cluster-randomized trials.⁴⁸ The process of participant enrollment and flow throughout the study will be summarized using a flow-diagram. Participant demographics and baseline outcome variables will be summarized using descriptive summary measures expressed as mean (standard deviation) or median (interquartile range) for continuous variables depending on the distribution, and number (percent) for categorical variables.⁴⁹ An ITT principle will be adopted to analyze all outcomes and the unit of analysis will be the individual participants. Missing data will be assumed to be missing at random and will be handled with multiple imputation.^{50,51}

The primary analysis will compare the treatment groups using the SSI outcome and the secondary analysis will compare the unplanned fracture-related reoperation outcome. The secondary comparison will be conducted in accordance with best practice guidelines for secondary analyses. For all models, the results will be expressed as relative measure of effect (odds, risk, or hazard ratios) and corresponding two-sided 95% confidence intervals.

5.2.2 Analysis of the Study Outcomes

Adopting an ITT principle, multilevel regression models will be used. Correlation structures will be fit based on the observed between cluster and between period effects. A robust sandwich estimator will be used to analyze the primary and secondary outcomes.

For the primary outcome, SSI will be the dependent variable and the antiseptic solution (treatment group) will be the independent variable. For the secondary outcome, unplanned fracture-related reoperation will be the dependent variable and the antiseptic solution (treatment group) will be the independent variable. For both analyses, multiple imputation will be used to handle missing data.⁵¹

As the optimal methods for analyzing cluster crossover trials continue to evolve, the final statistical modeling technique to be used will be determined in accordance with contemporary best practices prior to the completion of participant follow-up. A separate Statistical Analysis Plan will be developed prior to study closeout. **Table 7** below shows a summary of the study outcomes, corresponding hypotheses, and currently proposed methods of analysis.

Table 7: Summary of Outcome Analysis Plan

Objective	Outcome		Hypothesis	Method of Analysis
	Name	Type		
To determine the effect of iodine-based versus CHG-based pre-operative antiseptic skin solutions on the incidence of SSI and unplanned fracture-related reoperation.	SSI	Binary	Iodine solution will be more effective than CHG solution	Multi-level regression model
	Unplanned Fracture-Related Reoperation	Binary	Iodine solution will be more effective than CHG solution	Multi-level regression model

Note: CHG = chlorhexidine gluconate; SSI = Surgical Site Infection

5.2.3 Subgroup Analyses

A limited number of *a priori* subgroup analyses will be performed. The open fracture subgroups will include: i) severity of open fracture wound (Gustilo-Anderson type I or II versus III);¹ ii) upper extremity versus lower extremity open fractures; iii) none, minimal, or surface contamination versus contamination embedded in bone or deep soft tissues;³⁴ and, iv) presence or absence of comorbidities that affect wound healing.

The closed fracture subgroups of interest include: i) severe soft tissue injury (Tschirne Grade 3 versus Tschirne Grade 0-2) and, ii) presence or absence of comorbidities that affect wound healing. These analyses will be performed by comparing the effect estimates in both groups (interaction effect). We hypothesize that effect will differ by subgroup. These analyses will be approached and reported in accordance with best practices and guidelines for subgroup analyses.^{33,52-54} **Table 8** below shows a summary of the subgroup analysis objectives, corresponding outcomes, hypotheses, and methods of analysis for each fracture population.

Table 8: Summary of Subgroup Analysis Plan

Objective	Outcome		Hypothesis	Method of Analysis
	Name	Type		
Open Fracture Subgroup Analyses				

Objective	Outcome		Hypothesis	Method of Analysis
	Name	Type		
Severity of open fracture (Gustilo-Anderson Type I or II vs. Type III)	SSI / Unplanned Fracture-Related Reoperation	Binary	Iodine solution will be associated with a larger reduction in odds for SSI and reoperation than CHG solution in more severe fractures	Interaction of treatment by subgroup
Upper extremity vs. lower extremity fractures	SSI / Unplanned Fracture-Related Reoperation	Binary	Iodine solution will be associated with a larger reduction in odds for SSI and reoperation than CHG solution in lower extremity compared to upper extremity fractures	Interaction of treatment by subgroup
None, minimal, or surface wound contamination vs. embedded wound contamination	SSI / Unplanned Fracture-Related Reoperation	Binary	Iodine solution will be associated with a larger reduction in odds for SSI and reoperation than CHG solution in embedded contaminated wounds compared to wounds with no, minimal or surface contamination	Interaction of treatment by subgroup
Presence or absence of comorbidities that affect wound healing	SSI / Unplanned Fracture-Related Reoperation	Binary	Iodine solution will be associated with a larger reduction in odds for SSI and reoperation than CHG solution in participants who have comorbidities that affect wound healing	Interaction of treatment by subgroup
Closed Fracture Subgroup Analyses				
Severe soft tissue injuries (Tscherne Grade 3 vs. Tscherne Grade 0-2)	SSI / Unplanned Fracture-Related Reoperation	Binary	Iodine solution will be associated with a larger reduction in odds for SSI and reoperation than CHG solution in fractures with severe soft tissue injuries	Interaction of treatment by subgroup
Presence or absence of comorbidities that affect wound healing	SSI / Unplanned Fracture-Related Reoperation	Binary	Iodine solution will be associated with a larger reduction in odds for SSI and reoperation than CHG solution in participants who have comorbidities that affect wound healing	Interaction of treatment by subgroup

Note: CHG = chlorhexidine gluconate; SSI = Surgical Site Infection

